Comparing the efficacy of cardiac rehabilitation for patients with peripheral artery disease to patients with coronary artery disease/Protocol #03

**List of Abbreviations/ Terminology (in alphabetical order)**

6MWT	6 Minute Walk Test
CAD	Coronary Artery Disease
CLI	Critical Limb Ischemia
CI	Confidence Interval
ES	Effect Size
IC	Intermittent Claudication
ICC	Intraclass Correlation Coefficient
PAD	Peripheral Artery Disease
SF-36	Short Form-36 Health Survey
QOL	Quality of Life
TRI	Toronto Rehabilitation Institute
VO2peak	Peak Oxygen Consumption
WIQ	Walking Impairment Questionnaire

**Protocol Summary**

**COMPARING THE EFFICACY OF CARDIAC REHABILITATION FOR PATIENTS WITH PERIPHERAL ARTERY DISEASE TO PATIENTS WITH CORONARY ARTERY DISEASE**

*Short Title:* Exercise for PAD

*Clinical Phase / Type of Study:* Phase IV

**Sample Size**

N= 28 x 2 groups (coronary artery disease (CAD) and peripheral artery disease (PAD))

**Study Population**

Patients diagnosed with PAD, CAD or concomitant PAD and CAD. Patients with vascular aneurysms, chronic heart failure, cancer, stroke, respiratory disease, chronic kidney disease, foot ulcers/skin breakdowns which may impede ability to exercise and patients who cannot follow instructions in English will be excluded

**Accrual Period**

January 2018 – June 2018

Comparing the efficacy of cardiac rehabilitation for patients with peripheral artery disease to patients with coronary artery disease/Protocol #03

### **Study Design**

This study is a prospective two-arm cohort study with both groups (CAD and PAD) undergoing the same intervention (standard 6 month out-patient cardiac rehabilitation program offered at the Toronto Rehabilitation Institute Rumsey Centre).

### **Study Duration**

January 2018- December 2018

### **Study Agent/ Intervention/ Procedure**

The standard out-patient cardiac rehabilitation program involves weekly 1.5 hour visits at the Toronto Rehabilitation Institute Rumsey Centre for 6 months. Each visit will consist of an exercise component as well as a risk factor education lecture. Prior to the start of the program, participants will attend two assessment sessions with cardiac rehabilitation staff members to review medical history as well as complete a cardiopulmonary exercise test. During the cardiac rehabilitation program, participants will walk at 60-80% of their VO2peak heart rate based on the results of their exercise test, as per standard care procedures. Adjustments will be made to the patient's exercise prescription as their fitness improves under the discretion of the cardiac rehabilitation supervisor, as per standard care procedures. Patients will also be asked to exercise an additional four times during the week on their own time for a total of five times per week, as per standard care procedures.

### **Primary Objective**

The primary objective of this proposed study is to compare the magnitude of the responses to a 6-month cardiac rehabilitation program for patients with PAD in contrast to patients with CAD. The primary variable of interest will be peak oxygen consumption (VO2peak) with a secondary variable of interest being functional capacity, as measured by the 6-minute walk test. Tertiary variables of interest will include walking impairment, as measured by the Walking Impairment Questionnaire, and quality of life, as measured by the Short Form-36 health survey (SF-36).

**Secondary Objective** The second objective of this proposed study is to determine if the magnitude of responses to cardiac rehabilitation for patients with PAD are dependent on biological sex or type of PAD (asymptomatic, post-surgical intervention, or intermittent claudication).

**Exploratory Objectives** Exploratory objectives include comparing acute exercise responses (prescribed exercise training load, actual training load, exercising heart rate and rating of perceived exertion) between PAD and CAD patients.

**Endpoints of the study** This study will allow for the comparison of the efficacy of cardiac rehabilitation for CAD and PAD patients to provide further support of the application of exercise rehabilitation for PAD patients. In addition, this study will inform future studies investigating optimal exercise prescriptions for PAD patients.

Comparing the efficacy of cardiac rehabilitation for patients with peripheral artery disease to patients with coronary artery disease/Protocol #03

## **1.0 General Information**

1.1 Protocol title and date.

Comparing The Efficacy Of Cardiac Rehabilitation For Patients With Peripheral Artery Disease To Patients With Coronary Artery Disease -November 30, 2017

## **2.0 Background Information**

2.1 A summary of previous literature

Patients and clinicians have expressed an interest in the use of nonpharmacological interventions for health management (Crowe et al., 2015). Exercise is commonly recommended as a treatment for patients who present with any type of peripheral artery disease (PAD) (Hernando & Conejero, 2007; Ouriel 2001). In fact, participation in exercise programs for treatment of intermittent claudication (IC), which is a hallmark symptom of PAD consisting of pain with walking, is considered a gold standard (Thukkani & Kinlay, 2015). There is strong evidence to support the efficacy of exercise training in improving functional capacity and symptoms for patients with asymptomatic and symptomatic PAD (Class of recommendation I, level of evidence A) (Gerhard-Herman et al., 2017).

The AHA/American College of Cardiology recommend supervised exercise at least three times a week, 30-45 minutes per session for at least 12 weeks for patients with PAD (Gerhard-Herman et al., 2017). All sessions should begin and end with a warm-up and cool-down period, respectively. In contrast, the Canadian Guidelines for Cardiac Rehabilitation and Cardiovascular Disease Prevention recommend PAD patients with IC to exercise for 2 to 5 minutes close to their claudication pain threshold with intermittent breaks of 1 to 2 minutes of passive recovery (Canadian Association of Cardiac Rehabilitation, 2009). Patients should be encouraged to exercise at least three times a week with a goal of gradually decreasing resting time while increasing exercise time (Canadian Association of Cardiac Rehabilitation, 2009). Recommendations specifically for asymptomatic PAD patients are currently unclear.

Supervised programs, similar to cardiac rehabilitation, have been recommended for patients with PAD as first-line therapy prior to consideration for surgical interventions (Milani & Lavie, 2007). Previous research has suggested that exercise programs which utilize a mix of aerobic and resistance exercise tend to result in greater improvements in walking capacity for patients with PAD (Parmenter et al., 2015). In addition, vigorous intensity exercise training leads to greater improvements in VO2peak (mean difference

## Comparing the efficacy of cardiac rehabilitation for patients with peripheral artery disease to patients with coronary artery disease/Protocol #03

1.42 ml/kg/min, 95% CI: 1.04 to 1.80,  $p<0.00001$ ) compared to moderate intensity exercise (mean difference = 0.43/ml/kg/min, 95% CI 0.01 to 0.85,  $p =0.05$ ) (Parmenter et al., 2015). Although optimal exercise prescriptions for patients with PAD remain unclear (Parmenter et al., 2015), cardiac rehabilitation programs consisting of progressive intensity aerobic and resistance exercises appear to be a good starting point. Patients with IC may participate in an interval-style walking program where walking duration and rest periods are defined by pain tolerance and the time it takes for the pain to subside (Hamburg & Balady, 2011). Conversely, patients without IC are recommended to exercise continuously for 30 to 60 minutes per session at a moderate intensity (Hamburg & Balady, 2011).

Exercise appears to be an excellent addition to medical therapy and revascularization procedures. In a randomized trial of patients with aortoiliac PAD, peak walking time improved the greatest among patients who underwent supervised exercise and optimal medical therapy for 6 months compared to patients who underwent stent revascularization with optimal medical therapy and patients who underwent medical therapy alone ( $\Delta 5.8\pm4.6$ ,  $\Delta 3.7\pm4.9$ , and  $\Delta 1.2\pm2.6$  minutes, respectively,  $P<0.05$ ) (Murphy et al., 2012). This suggests that exercise can lead to greater functional improvements than endovascular procedures when combined with optimal pharmacological interventions. In a trial with femoropopliteal PAD patients randomized to angioplasty, supervised exercise or angioplasty and supervised exercise, all participants had an improvement in IC distance when assessed at the three month follow-up (Mazari et al., 2010). Nevertheless, patients randomized to supervised exercise and angioplasty had the greatest improvement compared to patients randomized to exercise alone and angioplasty alone ( $\Delta 108$ ,  $\Delta 61.2$ ,  $\Delta 59$  meters, respectively,  $P<0.05$ ). A clinically relevant improvement in walking distance for patients with PAD is considered greater than 100m (Hamburg & Balady, 2011). Exercise and endovascular intervention have statistically and clinically significant increases in walking distance. Improvements in QOL were also observed in all groups (effect size  $>0.5$ ) (Mazari et al., 2010). Considering the strong evidence, exercise should be automatically recommended in combination with endovascular interventions and/or pharmacological therapy.

Exercise rehabilitation has been shown to improve walking ability among PAD patients (Haas, Lloyd, Yang & Terjung, 2012; Januszek et al., 2014; McDermott et al., 2013). Exercise training can result in two-fold increases in walking time (Bonaca & Creager, 2015). Clinically significant improvements in walking time have been defined as an increase of 5 minutes for patients with PAD (Hamburg & Balady, 2011). Januszek et al. (2014) observed a significant change in walking time from  $470.8\pm187.1$  seconds at baseline to  $898.0 \pm 358.7$  ( $P<0.001$ ) 12-week treadmill training program 3 times a week for patients with IC. Remarkably, improvements in maximal walking time were sustained at follow-up (mean 37 weeks) compared to baseline with clinical and statistical significance ( $470.8\pm187.1$  seconds vs.  $775.4\pm 345.4$  seconds,  $P<0.001$ ). Small but statistically significant improvements in relative  $VO_2$ peak for PAD patients in exercise rehabilitation have also been observed compared to control patients who did not participate in exercise rehabilitation ( $\Delta=0.62$  ml/kg/min (95%CI 0.47 to 0.77,  $P<0.00001$ ) (Parmenter et al., 2015). The training responses across different clinical presentations of

Comparing the efficacy of cardiac rehabilitation for patients with peripheral artery disease to patients with coronary artery disease/Protocol #03

PAD (asymptomatic, intermittent claudication (IC), critical ischemia (CLI)) are difficult to compare due to various training protocols and limited exercise training data with asymptomatic and CLI patients .

Patients with coronary artery disease (CAD) undergoing exercise rehabilitation also have significant benefits including a lower risk for cardiovascular mortality (RR=0.74, 95%CI 0.63 to 0.87), fewer hospitalizations (RR=0.69, 95%CI 0.51 to 0.93) and improvements in functional capacity as measured by the 6 minute walk test (6MWT) ( $\Delta=60.43\text{m}$ , 95%CI 54.57 to 66.30m) (Bellet et al., 2012; Heran et al., 2011). In a prospective cohort study with 29 CAD patients undergoing cardiac rehabilitation, there was a significant improvement in  $\text{VO}_2\text{peak}$  ( $\Delta=2.45 \pm 0.5 \text{ mL/kg/min}$ ,  $P<0.001$ ) (Lucini et al., 2002). Greater improvements in  $\text{VO}_2\text{peak}$  were observed in a meta-analysis of CAD patients in cardiac rehabilitation compared to CAD patients who did not participate in cardiac rehabilitation (mean difference = 3.22ml/kg/min, 95%CI 2.42 to 4.03,  $P<0.01$ ) (Tang, Fu, Zhang, & Zhang, 2014). In spite of the results suggesting that CAD patients have greater improvements in  $\text{VO}_2\text{peak}$  following cardiac rehabilitation compared to PAD patients, there is large variability in exercise prescriptions applied limiting the strength of that conclusion.

Although a great deal of research has supported the efficacy of exercise rehabilitation for PAD, it is infrequently implemented into clinical practices (Milani & Lavie, 2007). In an analysis of the medical treatments accessed by PAD patients, exercise or diet counselling were only used in 22% of visits (Berger & Ladapo, 2017). Implementing risk factor education and exercise rehabilitation programs for patients with PAD would be consistent with the Chronic Care Model to help manage chronic diseases (Lovell, Meyers, Forbes, Dresser, & Weiss, 2011). The integration of the Vascular Clinic at the Toronto Rehabilitation Institute (TRI) will help to provide opportunities of exercise rehabilitation for patients with PAD.

To date, no comparison of cardiac rehabilitation efficacy and acute exercise responses has been made between patients with PAD and patients with CAD. Considering some of the parallels between the two conditions, as they are both atherosclerotic conditions, and the strong recommendations for exercise in both populations, it is worthwhile to compare the efficacy of cardiac rehabilitation responses. It is also unclear if the magnitude of response for PAD patients is dependent on biological sex and clinical presentation as this may influence the development of exercise prescriptions. This proposed study, which is in the process of being registered with clinicaltrials.gov, hopes to address these gaps in the literature.

## 2.2. Rationale for the study

It is unclear if cardiac rehabilitation will be as effective for patients with PAD as it is for improving the function and health outcomes of patients with CAD. While there are common pathological traits of CAD and PAD, there are some distinct features that are evident in pathology. Acute responses to exercise have yet to be compared between

## Comparing the efficacy of cardiac rehabilitation for patients with peripheral artery disease to patients with coronary artery disease/Protocol #03

patient populations. As well, differences in responses to cardiac rehabilitation based on biological sex and clinical presentation of PAD are not well established. With the newly implemented cardiac rehabilitation program specifically for patients with PAD at TRI, this proposed study is aligned well to address these gaps in the literature. This trial will be conducted in compliance with the protocol described below as well as ICH and GCP standards.

This research is important as the findings from this study may provide further support for the implementation of PAD-specific exercise rehabilitation programs. Determining the efficacy of cardiac rehabilitation for patients with PAD can also help contribute to the understanding of PAD in relation to exercise. Lastly, determining if the magnitude of response is dependent on biological sex and presentation of PAD can help guide future research in determining optimal exercise prescriptions

### 2.3 Potential Benefits

Patients, the community, and the institution will not benefit directly from this research study as the research intervention is standard care procedures which has been provided to all patients of the Cardiovascular Prevention and Rehabilitation Program at TRI for decades.

The research community will likely benefit from the knowledge gained in this research to help better understand exercise for individuals living with PAD. In addition, this research may inform future research regarding exercise prescriptions for individuals living with PAD.

### 2.4 Description of the population to be studied.

Inclusion criteria will include patients over the age of 18 that have been diagnosed with lower extremity PAD or CAD. Patients with concomitant CAD and PAD will also be included in the study. Group allocation will be based on referring diagnosis. In addition, patients must be able to access and participate in the cardiac rehabilitation program at the TRI.

Patients diagnosed with PAD from the University Health Network and Sunnybrook Hospital will be referred by vascular surgeons to the TRI Rumsey Centre for cardiac rehabilitation. Patients with CAD referred to cardiac rehabilitation will be identified through consented chart review and invited to participate in the study.

Patients with vascular aneurysms, chronic heart failure, cancer, stroke, respiratory disease, or chronic kidney disease will be excluded. Patients with foot ulcers or skin breakdowns which may impede ability to exercise will also be excluded. Patients who cannot follow instructions in English will be excluded. Patients who attend less than 70% of sessions of the weekly sessions at TRI (<10 sessions in total) will be excluded from the main analysis and included in an intention-to-treat analysis.

All patients will provide written informed consent prior to study participation. Patients identified with PAD will be referred by their vascular surgeons from Toronto General

## Comparing the efficacy of cardiac rehabilitation for patients with peripheral artery disease to patients with coronary artery disease/Protocol #03

Hospital to the TRI cardiac rehabilitation program. Upon the initial assessment at TRI, PAD patients will be informed about participating in the proposed study by the principal investigator. CAD patients who have attended an initial assessment and have consented to chart review will have their patient file reviewed to determine if the patient is an appropriate match to a PAD patient based on sex, age, presence of diabetes, and assigned cardiac rehabilitation supervisor. One of the study investigators will then inform the patient during their second assessment at TRI about the study and invite the patient to participate in the study.

### **3.0 Study Objectives and Hypothesis**

3.1 A description of the objectives and the purpose of the study.

The purpose of this study is to compare the efficacy of a 6-month out-patient cardiac rehabilitation program for patients with CAD to patients with PAD.

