#### 3.1.1 Primary objective

The primary objective of this proposed study is to compare the magnitude of the responses to a 6-month cardiac rehabilitation program for patients with PAD in contrast to patients with CAD. The primary variable of interest will be peak oxygen consumption ( $VO_2\text{peak}$ ) with a secondary variable of interest being functional capacity, as measured by the 6-minute walk test. Tertiary variables of interest will include walking impairment, as measured by the Walking Impairment Questionnaire, and quality of life, as measured by the Short Form-36 health survey (SF-36).

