## **4.0 Study Design**

### **4.1 Primary and secondary endpoints**

Patients will undergo a baseline assessment with a laboratory technician involving a standard battery of measurements and questionnaires for characteristic purposes including anthropometrics, resting blood pressure, resting heart rate, smoking status, diabetes status, current exercise regimen, and current medications. During this assessment, clinicians will review previous and ongoing medical treatment (i.e. surgical procedures, next physician visit, ankle-brachial index measurement), presence of angina, and conduct resting 12-lead electrocardiograms. This will be followed by a medical assessment by a physician to further review medical history and safety precautions for exercise. Patients will be sent home with a walking impairment questionnaire (WIQ) (McDermott et al., 1998) and a quality of life (QOL) questionnaire (SF-36) (Brazier et al., 1992) to be submitted at their next visit. A requisition for blood work will also be given to patients to be completed prior to their second visit to determine HbA1c and total cholesterol levels.

During the second visit patients will undergo a maximal cardiopulmonary exercise test to determine cardiorespiratory fitness as measured by VO2peak and will also have an exercising 12-lead electrocardiogram. The cardiopulmonary exercise test will consist of a Bruce or modified Bruce treadmill protocol (Noonan and Dean, 2000).

After determining baseline VO2peak, an individualized walking exercise prescription will be developed by a cardiac rehabilitation supervisor which corresponds to approximately 60 to 80% of VO2peak. Patients will be invited to attend weekly 90-minute supervised exercise and education sessions at the same time every week for six months, as per standard care procedures. Patients will be encouraged to gradually increase their exercise time per session as well as frequency of sessions per week.

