### 4.2 Study Design

This study will be an interventional two-arm prospective cohort study. Both arms (PAD and CAD participants) will undergo the same standard 6 month out-patient cardiac rehabilitation program.

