## **5.0 Selection of Subjects**

### 5.1 Subject inclusion criteria.

Inclusion criteria will include patients over the age of 18 that have been diagnosed with lower extremity PAD or CAD. Patients with concomitant CAD and PAD will also be included in the study. Group allocation will be based on referring diagnosis. In addition, patients must be able to access and participate in the cardiac rehabilitation program at the TRI.

In order to compare patients with PAD to patients with CAD and to control for confounding variables, matching will be based on biological sex, age ( $\pm 5$  years), presence of diabetes (yes or no), smoking status (current, previous, never), and cardiac rehabilitation supervisor.

Patients diagnosed with PAD from the University Health Network and Sunnybrook Hospital will be referred by vascular surgeons to the TRI Rumsey Centre for cardiac rehabilitation. Patients with CAD referred to cardiac rehabilitation will be identified through consented chart review and invited to participate in the study.

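### The PAD–CAD contrast in pre-post change mixes program effect with background change and post-procedure recovery, so it cannot be reported as a difference in rehabilitation efficacy

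*Combined protocol and SAP*

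**What the plan says.** The stated purpose in section 3.1 is to "compare the efficacy of a 6-month out-patient cardiac rehabilitation program for patients with CAD to patients with PAD". The title and the summary paragraph on study endpoints also speak of efficacy. The primary objective in 3.1.1 is worded differently: to "compare the magnitude of the responses to a 6-month cardiac rehabilitation program for patients with PAD in contrast to patients with CAD".

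On design, section 4.2 states: "Both arms (PAD and CAD participants) will undergo the same standard 6 month out-patient cardiac rehabilitation program". Section 5.1 adds: "Group allocation will be based on referring diagnosis". No untreated group and no run-in period is described.

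Eligibility in 5.1 covers "patients over the age of 18 that have been diagnosed with lower extremity PAD or CAD", and the exclusions in 5.2 set no window around an event or procedure. Matching in 5.1 uses biological sex, age within 5 years, "presence of diabetes (yes or no), smoking status (current, previous, never), and cardiac rehabilitation supervisor". The primary analysis in 8.1 is a 2 (time) by 2 (group) ANOVA with no covariates.

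At the baseline assessment in 4.1, "clinicians will review previous and ongoing medical treatment (i.e. surgical procedures, next physician visit, ankle-brachial index measurement". The data items in 4.8 include type of PAD or CAD, but no date of an event or procedure. The PAD types in 3.1.2 include a post-surgical category.

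**The concern.** Each arm's change from baseline to month 6 is the program effect plus whatever would have happened anyway: natural course, recovery from a recent event or procedure, concurrent treatment, and familiarity with the tests. The time-by-group interaction equals a difference in program effect only if the rest is the same, on average, in PAD and CAD. Nothing in the design secures or tests that equality. The groups are formed by diagnosis, recency is left free in both arms, and section 4.3 on bias deals only with patient blinding and the order of ankle-brachial measurements.

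A significant interaction would be read as rehabilitation working better in one disease than the other. A null result would be read as rehabilitation working equally well. Section 2.2 expects the findings to bear on support for PAD-specific programs, so the reading matters. If event and procedure dates are not put on the data sheet prospectively, confounding by recency may be impossible to examine afterwards.

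**Working it through.** **1. What the contrast estimates.** Write the mean change in each arm as P (program effect) + B (background change, including recovery).

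- Observed contrast = (P_CAD + B_CAD) − (P_PAD + B_PAD) = (P_CAD − P_PAD) + b, where b = B_CAD − B_PAD.
- With two time points, the time-by-group interaction test is the two-sample t-test on change scores. It tests the sum and cannot separate the two terms.

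**2. Where b could be controlled.**

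| Place in the plan | Time since event or procedure |
|---|---|
| Eligibility (5.1, 5.2) | No window |
| Matching (2.4, 5.1, 11.1) | Not a factor |
| Data items (4.8) | No date listed |
| Primary ANOVA (8.1) | No covariates |
| Baseline review (4.1) | Procedures reviewed clinically; timing is not a study variable |

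**3. The plan's own sample size (8.2).** Inputs: 10 m difference, SD 12 m (the spread quoted with the CAD walk-test change; the plan does not label it as the SD used), two-sided alpha 0.05, power 0.80.

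- n = 2 × (1.960 + 0.842)² × 12² / 10² = 22.6, so 23 per group. This reproduces the stated figure.

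**4. Implied SD for VO2peak.** Section 8.2 gives 1.6 ml/kg/min as detectable with 28 per group and states no SD.

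- Normal approximation: SD = 1.6 / [(1.960 + 0.842) × √(2/28)] = 2.14.
- With the t distribution: 2.10. I use 2.1.

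**5. Illustration.** Assumptions: the program effect is identical in both diseases; SD of change is 2.1; 22 per group complete (28 × 0.8 = 22.4). The documents give no value for b, so a range is shown, starting at zero.

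- Standard error = 2.1 × √(2/22) = 0.633. Critical t on 42 df = 2.018.
- Noncentrality = |b| / 0.633. Rejection probability comes from the noncentral t.

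| Net background difference, either direction (ml/kg/min) | Noncentrality | P<0.05, 22 per group | P<0.05, 28 per group |
|---|---|---|---|
| 0 | 0 | 5% | 5% |
| 0.5 | 0.79 | 12% | 14% |
| 1.0 | 1.58 | 34% | 42% |

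The rates are the same for b and −b; only the sign of the spurious finding changes. A larger sample raises the rate and does not remove the bias. The term can also hide a real effect: a true program difference of 1.6 in favour of CAD, with a background difference of 1.0 in favour of PAD, leaves an expected contrast of 1.6 − 1.0 = 0.6.

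**The case against.** **The plan is openly a cohort study, and its working language is already about change.** The primary objective speaks of the magnitude of responses, the endpoints in 4.1 are changes, and 8.1 tests for greater improvements. The program is standard care, so an untreated arm is not a realistic request. Matching is there explicitly to control confounding. This largely stands: the objective in 3.1.1 can be answered descriptively. What it does not rescue is the efficacy wording in 3.1 and the summary. Matching also leaves recency out.

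**A reader might infer that the bias favours the hypothesised CAD advantage.** The documents do not support that. Nowhere do they say that CAD participants are recently post-event, and they give no recovery rate. The PAD arm includes post-surgical patients referred by vascular surgeons, whose recovery could push the contrast the other way. If recovery is equal in both arms, b is zero.

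**A reader might take the 6-month randomised trial in 2.1 as evidence of spontaneous recovery**, since walking time also rose in "patients who underwent stent revascularization with optimal medical therapy and patients who underwent medical therapy alone". Those are PAD patients, both groups were on active treatment, and the outcome was peak walking time. The trial says nothing about untreated change in VO2peak, or about CAD.

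**A reader might also infer that natural recovery explains the literature behind the hypothesis.** Section 2.1 does set an uncontrolled CAD change of 2.45 ml/kg/min beside a controlled PAD difference of 0.62. But it also cites a controlled CAD difference of 3.22 (95% CI 2.42 to 4.03), from a meta-analysis whose title refers to patients after revascularisation. CAD may truly gain more, although section 2.1 itself warns that the exercise prescriptions varied. The point is that this study could not show it.

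**Adjustment has limits.** Many PAD and some CAD patients may have no index date. Recency may be closely tied to diagnosis. Adjusting for baseline between non-randomised groups is debatable. No adjustment replaces a comparator. All of this stands, and it is why the sensitivity analysis should be categorical and supportive only.

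**Conclusion.** The concern holds as a limit on interpretation. With no untreated comparator and no handling of time since event or procedure, the PAD–CAD difference in pre-post change is not an estimate of differential rehabilitation efficacy. It is a valid description of how much each cohort changed during the program.

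Direction and size are not fixed by the documents. The rates of 12% and 34% rest on an assumed net background difference of 0.5 or 1.0 ml/kg/min, an equal program effect, an SD back-calculated from the plan's 1.6 figure, and 22 completers per group. They show how sensitive the test would be to such a difference. They do not forecast one. That the design can produce a spurious or masked difference is supported; that it will do so, or in which direction, is not.

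**What to change.** 1. **Wording.** In the summary paragraph on study endpoints and in section 3.1, replace efficacy with change during the program, in line with 3.1.1. State there that the contrast does not estimate a difference in rehabilitation effect.
2. **Data.** Add two items to the data sheet in 4.8, for both arms: whether there was an index event or procedure, and its date. Take them from the history already reviewed at the first visit.
3. **Analysis.** In 8.1, pre-specify one sensitivity analysis of change by recency category (none, recent, remote), with the cut-off fixed before the data are examined and the same categories in both arms. Report the group difference and its confidence interval beside the primary result, as supportive only.

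The cost is a short chart extraction per patient, some wording and one extra model, with no added visits and no change to care. The downsides are a more modest headline claim, and an imprecise sensitivity estimate if recency is strongly associated with diagnosis. The analysis reduces one source of confounding and does not stand in for an untreated arm.
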